7.11.5 Other Observations Related to Safety

7.11.5.1 Displays of Treatment-Emergent Adverse Events (Japanese)

Analysis set:

Safety analysis set

Analysis variable(s):

TEAE

Analytical method(s):

The similar summaries as Section 7.11.1.2 will be provided for the above analysis variables. All summaries will be presented in Japanese.

7.12 Interim Analysis

At the time when the data from approximately 25 subjects are collected, the data until Week 12 in the Treatment Period will be analyzed. In addition, at the time when all subjects complete Week 24 in the Treatment Period, the data until Week 24 in the Treatment Period will be analyzed separately after being locked. These analyses will not intend to continue or discontinue this study.

The analyses at Week 12 will be performed only for items required to examine the study design for subjects aged less than 6 years in this statistical analysis plan. Specifically, they are 7.3.5, 7.3.6, 7.4, 7.5, 7.7.1, 7.7.2, 7.8.2, 7.8.4.7, 7.9.1 (1), 7.11.1, 7.11.1.2, (1), (4) to (11) (and the corresponding Japanese analysis [7.11.5.1]), and 7.11.2.1. The results of these analyses will be included in the consultation materials with regulatory authorities and not included in the clinical study report. Additional analyses may be performed in response to changes in the policy for preparing consultation materials or requests from regulatory authorities. In such cases, the statistical analysis plan will not be revised or the additional analysis plan will not be prepared.

7.13 Changes in the Statistical Analysis Plan

Although home blood pressure is defined as a safety endpoint in the protocol, it will be also evaluated as an efficacy endpoint as described in 7.8.3 in this statistical analysis plan.

8.0 REFERENCES

Not applicable.

9.0 APPENDIX

9.1 AEs of Special Interest

Table 9.a Hypotention-related AE

PT NAME	PT CODE
Bezold-Jarisch reflex	10076999
Blood pressure ambulatory decreased	10005731
Blood pressure decreased	10005734
Blood pressure diastolic decreased	10005737
Blood pressure immeasurable	10005748
Blood pressure orthostatic abnormal	10053354
Blood pressure orthostatic decreased	10053356
Blood pressure systolic decreased	10005758
Blood pressure systolic inspiratory decreased	10005761
Capillary leak syndrome	10007196
Cardiogenic shock	10007625
Cardiovascular insufficiency	10065929
Circulatory collapse	10009192
CT hypotension complex	10078280
Diastolic hypotension	10066077
Dizziness	10013573
Dizziness exertional	10013576
Dizziness postural	10013578
Hypoperfusion	10058558
Hypotension	10021097
Hypotensive transfusion reaction	10072264
Hypovolaemia	10021137
Hypovolaemic shock	10021138
Mean arterial pressure decreased	10026983
Mesenteric traction syndrome	10069699
Neonatal hypotension	10049223
Obstructive shock	10073708
Orthostatic hypotension	10031127
Orthostatic intolerance	10063927
Presyncope	10036653
Procedural hypotension	10062300
Shock	10040560
Shock haemorrhagic	10049771
Shock symptom	10040581
Syncope	10042772
Vascular resistance systemic decreased	10047106
Vasoplegia syndrome	10067080
Loss of consciousness	10024855
Vertigo	10047340

MedDRA Version 21.0

Table 9.b Renal Dysfunction-related AE

PT_CODE	PT_NAME
10069339	Acute kidney injury
10069688	Acute phosphate nephropathy
10002847	Anuria
10003885	Azotaemia
10066338	Continuous haemodiafiltration
10061105	Dialysis
10078987	Foetal renal impairment
10018875	Haemodialysis
10053090	Haemofiltration
10077515	Hyponatriuria
10049778	Neonatal anuria
10029155	Nephropathy toxic
10030302	Oliguria
10034660	Peritoneal dialysis
10072370	Prerenal failure
10038435	Renal failure
10038447	Renal failure neonatal
10062237	Renal impairment
10049776	Renal impairment neonatal

MedDRA Version 21.0

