7.5 Criteria for Discontinuation or Withdrawal of a Subject

The primary reason for discontinuation or withdrawal of the subject from the study or study drug should be recorded in the case report form (eCRF) using the following categories. For subject failure, refer to Section 9.1.14.

1. Death. The subject died on study.

Note: If the subject dies on study, the event will be considered as SAE. See Section 10.2.2 for the reporting procedures.

2. AE. The subject has experienced an AE that requires early termination because continued participation imposes an unacceptable risk to the subject's health or the subject is unwilling to continue because of the AE.

- Acute deterioration of renal function

Acute deterioration of renal function or increase in potassium value should be monitored carefully. If 50% reduction in estimated glomerular filtration rate [eGFR] or less than 30 mL/min/1.73 m², or serum potassium value over 5.5 mEq/L is seen at consecutive 2 time points, discontinuation should be considered. Appropriate follow-up should be performed for all subjects who discontinue the study until the subjects have been recovered or stabilized (see Section 9.1.9).

- Liver Function Test (LFT) Abnormalities

Study drug should be discontinued immediately with appropriate clinical follow-up (including repeat laboratory tests, until a subject's laboratory profile has returned to normal/baseline status, see Section 9.1.9), if the following circumstances occur at any time during study drug treatment:

- ALT or AST > 8 × ULN, or
- ALT or AST > 5 × ULN and persists for more than 2 weeks, or
- ALT or AST > 3 × ULN in conjunction with elevated total bilirubin > 2 × ULN or international normalized ratio (INR) > 1.5, or
- ALT or AST > 3 × ULN with appearance of fatigue, nausea, vomiting, right upper quadrant pain or tenderness, fever, rash and/or eosinophilia (> 5%).

3. Protocol deviation. The discovery after the start of the Treatment Period that the subject failed to meet protocol entry criteria or did not adhere to protocol requirements, and continued participation poses an unacceptable risk to the subject's health.

4. Lost to follow-up. The subject did not return to the clinic and attempts to contact the subject, the subject's parent or the subject's legal guardian were unsuccessful. Attempts to contact the

subject, the subject's parent or the subject's legal guardian must be documented in the subject's source documents.

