10.1.2 Additional Points to Consider for AEs

An untoward finding generally may:

- Indicate a new diagnosis or unexpected worsening of a pre-existing condition. (Intermittent events for pre-existing conditions or underlying disease should not be considered AEs.)
- Necessitate therapeutic intervention.
- Require an invasive diagnostic procedure.
- Require discontinuation or a change in dose of study drug or a concomitant medication.
- Be considered unfavorable by the investigator or subinvestigator for any reason.
- AEs caused by a study procedure (eg, a bruise after blood draw) should be recorded as an AE.

Diagnoses vs signs and symptoms:

- Each event should be recorded to represent a single diagnosis. Accompanying signs (including abnormal laboratory values or ECG findings) or symptoms should NOT be recorded as additional AEs. If a diagnosis is unknown, sign(s) or symptom(s) should be recorded appropriately as an AE(s).

Laboratory values and ECG findings:

- Changes in laboratory values or ECG parameters are only considered to be AEs if they are judged to be clinically significant (i.e., if some action or intervention is required or if the investigator or subinvestigator judges the change to be beyond the range of normal physiologic fluctuation). A laboratory re-test and/or continued monitoring of an abnormal value are not considered an intervention. In addition, repeated or additional noninvasive testing for verification, evaluation or monitoring of an abnormality is not considered an intervention.
- If abnormal laboratory values or ECG findings are the result of pathology for which there is an overall diagnosis (eg, increased creatinine in renal failure), the diagnosis only should be reported appropriately as an AE.

Pre-existing conditions:

- Pre-existing conditions (present at the time of signing of informed consent) are considered concurrent medical conditions and should NOT be recorded as AEs. Baseline evaluations (eg, laboratory tests, ECG, X-rays etc.) should NOT be recorded as AEs unless related to study procedures. However, if the subject experiences a worsening or complication of such a concurrent medical condition after informed consent is signed, the worsening or complication should be recorded appropriately as an AE. The investigator or subinvestigator should ensure that the event term recorded captures the change in the condition (eg, “worsening of ...”).

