10.2.1.3 AEs of Special Interest Reporting

Pediatric subjects, the subject population of this study, are vulnerable, and as such need special attention with regard to the risk of the over decrease in blood pressure accompanying the use of antihypertensive drugs. Furthermore, kidney function is often impaired in pediatric subjects with secondary hypertension. Administration of RAS inhibitors to such patients may reduce GFR, deteriorating the kidney function. Hence, the following adverse events related to hypotension or renal impairment will be investigated as special interest AEs in this study.

[Hypotension-related AE]

Hypotension, blood pressure decreased, orthostatic hypotension, blood pressure orthostatic decreased, dizziness, dizziness postural, vertigo, circulatory collapse, shock, loss of consciousness, syncope, and presyncope.

[Renal dysfunction-related AE]

Renal failure, acute renal failure, renal impairment, prerenal failure, acute prerenal failure, anuria, oliguria, nephropathy toxic, acute phosphate nephropathy, and azotaemia.

If this AE of special interest occurs during the Run-in Period, the Treatment Period or the Follow-up Period, it should be reported to the sponsor (described in the separate contact information list) immediately or within 1 business day of first onset or subject's notification of the event. Hypotension-related AE or renal dysfunction-related AE Form or an SAE Form should be completed, signed and/or sealed by the principal investigator, and reported to appropriate personnel in the separate contact information list within 10 business days.

The AE of special interest have to be recorded as AEs in the eCRF. An evaluation form along with all other required documentation must be submitted to the sponsor.

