7.11.1.2 Displays of Treatment-Emergent Adverse events

Analysis set:

Safety analysis set

Analysis variable(s):

TEAE

Categories:

Intensity [Mild, Moderate, Severe]

Time of onset (day) $[1 \le - \le 14, 15 \le - \le 28, 29 \le - \le 42, 43 \le - \le 56, 57 \le - \le 70, 71 \le - \le 84, 85 \le - \le Max]$ $[1 \le - \le 84, 85 \le - \le 168, 169 \le - \le 252, 253 \le - \le 336, 337 \le - \le 420, 421 \le - \le Max]$

Analytical method(s):

The following summaries will be provided for the above analysis variables using frequency distributions by weight group ($< 50 \text{ kg}, \ge 50 \text{ kg}$) and in the combined weight groups.

TEAEs will be coded using MedDRA and will be summarized based on SOCs and PTs. SOCs will be sorted alphabetically and PTs will be sorted in decreasing frequency for tables provided by SOC and PT. SOC and PT will be sorted in decreasing frequency for tables provided by SOC only or PT only.

See "9.0 APPENDIX" for definitions of the TEAEs related to hypotension and renal dysfunction.

- (1) All TEAEs by SOC and PT
- (2) All TEAEs by SOC
- (3) All TEAEs by PT
- (4) Drug-related TEAEs by SOC and PT
- (5) Intensity of all TEAEs by SOC and PT
- (6) Intensity of drug-related TEAEs by SOC and PT
- (7) TEAEs leading to study drug discontinuation by SOC and PT
- (8) Serious TEAEs by SOC and PT
- (9) All TEAEs by SOC and PT over time
- (10) TEAEs related to hypotension by SOC and PT
- (11) TEAEs related to renal dysfunction by SOC and PT
- (12) Non-serious TEAEs whose incidence summarized by PT is \geq 2% by SOC and PT

The frequency distribution and incidence will be provided according to the rules below:

[Number of subjects]

- In case of "summaries by SOC and PT, by SOC only, or PT only"
 - A subject with multiple occurrences of TEAE within a SOC will be counted only once in that SOC. A subject with multiple occurrences of TEAE within a PT will be counted only once in that PT. Also, when calculating the percentages for TEAEs, the number of subjects in the safety analysis set will be used as the denominator.
- In case of "summaries of intensity by SOC and PT"

A subject with multiple occurrences of TEAE within a SOC or a PT will be counted only once for the TEAE with the maximum intensity. Also, when calculating the

percentages for TEAEs, the number of subjects in the safety analysis set will be used as the denominator.

• In case of "summaries by SOC and PT over time"

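### Renal adverse events recorded as laboratory changes without a diagnosis are left out of the SAP's grouped renal AE-of-special-interest table

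*SAP*

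**What the plan says.** Protocol 10.2.1.3 sets up two groups of AEs of special interest, hypotension and renal dysfunction. Its reason for the renal group is: "Administration of RAS inhibitors to such patients may reduce GFR, deteriorating the kidney function". The renal terms it then lists are: "Renal failure, acute renal failure, renal impairment, prerenal failure, acute prerenal failure, anuria, oliguria, nephropathy toxic, acute phosphate nephropathy, and azotaemia".

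The SAP turns this into a preferred-term list, "Table 9.b Renal Dysfunction-related AE" (Appendix 9.1). SAP 7.11.1.2 sends the reader to the appendix "for definitions of the TEAEs related to hypotension and renal dysfunction", and the table built from it is item ("11) TEAEs related to renal dysfunction by SOC and PT"). SAP 7.12 includes that item in the Week 12 analysis.

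Two rules in Protocol 10.1.2 decide how a renal laboratory finding becomes an AE. Where the abnormal value belongs to an overall diagnosis, "the diagnosis only should be reported appropriately as an AE". Where there is none, the other rule applies ("If a diagnosis is unknown, sign(s) or symptom(s) should be recorded appropriately as an AE(s"). In both cases the change must first be judged clinically significant.

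Protocol 7.5 places acute deterioration of renal function under the AE reason for discontinuation. Its trigger opens: "If 50% reduction in estimated glomerular filtration rate [eGFR] or less than 30 mL/min/1.73 m², or serum potassium value over 5.5 mEq/L", seen at two consecutive time points.

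**The concern.** The group is justified by a measured quantity, GFR, but neither list has a term for a change in that quantity or in creatinine. Protocol 10.1.2 allows a bare laboratory change to stand as an AE, so a valid renal AE can exist that the renal table cannot see.

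Safety is the primary objective, Protocol 6.2 expects many children with renal dysfunction, and renal events are one of only two groups singled out for special attention. Summary (11) is the only AE table that groups renal terms. If its definition is narrower than the concern it serves, a reader who relies on it sees too few affected children. The protocol list has the same gap, so a non-serious AE recorded this way also falls outside the special-interest reporting route in 10.2.1.3.

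**Working it through.** The documents give no figure to reproduce. The check compares the two lists, follows an event through the recording rules, and asks what the other outputs would show.

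**1. The lists.** The protocol has 10 renal terms and Table 9.b has 19 preferred terms. A search for creatinine, glomerular, GFR, filtration rate, urea, cystatin and clearance finds 0 of 10 and 0 of 19.

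Eight protocol terms recur word for word in Table 9.b; acute renal failure and acute prerenal failure do not. Table 9.b has 19 − 8 = 11 further terms:
- five dialysis or filtration procedures;
- four foetal or neonatal terms;
- acute kidney injury and hyponatriuria.

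The SAP therefore did not treat the protocol wording as fixed.

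**2. The comparison with hypotension.** Table 9.a includes measurement-type terms, such as decreased blood pressure, decreased systolic pressure and decreased mean arterial pressure. Table 9.b has no counterpart for GFR or creatinine.

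**3. Following one event.**

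| How a clinically significant GFR fall is recorded | In summary (11)? |
|---|---|
| Renal impairment, renal failure, acute kidney injury, azotaemia | Yes |
| GFR decreased or creatinine increased, no diagnosis | No |

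**4. What other outputs show.** A laboratory-coded AE still enters the all-TEAE tables (items 1 to 3) and, where applicable, the drug-related (4), discontinuation (7) and serious (8) tables. Under SAP 7.11.1.2 a subject is counted once within a system organ class and once within a preferred term. A child with two renal terms is therefore counted under each, and the number of distinct children cannot be found by adding rows.

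**5. The laboratory route.** SAP 7.11.2.1 gives summaries, case plots and shift tables for eGFR and creatinine. The markedly-abnormal-value limits in Table 9.c include eGFR < 30 and creatinine > 2.0 mg/dL, with no change-from-baseline rule. Halving eGFR gives 60 → 30, 90 → 45 and 110 → 55. Each meets the 50% figure in Protocol 7.5, and none is below 30.

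The creatinine limit helps only sometimes. Rearranging the formula in Protocol 9.1.9:

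creatinine = 110.2 × standard creatinine / (eGFR − 2.93)

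- Boy, 1.30 m (standard 0.402), eGFR 45: 110.2 × 0.402 / 42.07 = 1.05 mg/dL, not flagged.
- Boy, 1.70 m (standard 0.699), eGFR 45: 110.2 × 0.699 / 42.07 = 1.83 mg/dL, not flagged.
- Boy, 1.30 m, eGFR 30: 110.2 × 0.402 / 27.07 = 1.64 mg/dL, not flagged.
- Boy, 1.60 m (standard 0.602), eGFR 30: 110.2 × 0.602 / 27.07 = 2.45 mg/dL, flagged.

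So the laboratory counts are a partial backstop and do not replace a grouped AE count.

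**6. Scale.** One omitted child is 1/50 = 2 percentage points in the full study and about 1/25 = 4 points at Week 12. Purely as an assumption, 1 to 5 omitted children would be 2 to 10 points of 50. Nothing in the documents supports any particular number.

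**The case against.** The strongest reply is that little is hidden. Protocol 10.1.2 prefers the diagnosis, and its own example is a creatinine rise within renal failure. Protocol 7.5 gives sites a ready renal label for a marked eGFR fall. Table 9.b covers the main renal diagnoses and some findings that are not diagnoses (anuria, oliguria, hyponatriuria, azotaemia), so it is not the reverse of Table 9.a; both also carry neonatal terms that cannot apply here. The AE tables show laboratory-coded events by preferred term, and summary (11) is an SAP display that the safety analysis in Protocol 13.1.5 does not call for. Serious renal events have their own reporting route in Protocol 10.2.2. A narrow list can also be a deliberate choice for specificity.

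Most of this stands, and it rules out several stronger readings that a reader might infer:
- That the event motivating the list goes uncounted. Deterioration reported under a listed term is counted.
- That a child stopped under Protocol 7.5 disappears. If the AE led to stopping, it appears in item (7). The documents do not show that such a child would be recorded as a bare laboratory value. The 7.5 criterion also includes potassium, which the terms proposed here would not capture.
- That the Week 12 material would hide such events. SAP 7.12 also includes items (1) and (4) to (10) and the laboratory section.

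The reply does not remove the gap. Preferring the diagnosis does not help when there is none, which Protocol 10.1.2 expressly allows for. The SAP states no specificity rationale, and a list that admits oliguria and hyponatriuria is not confined to diagnoses. Separate rows would keep the narrow count visible in any case.

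**Conclusion.** The point holds in a limited form. Summary (11) does not give a complete, de-duplicated count of children with renal AEs, because AEs recorded as a GFR fall or creatinine rise without a diagnosis lie outside its definition. The events are missing from one grouping, not from the analysis.

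This assumes that some sites record such a change without a diagnosis, and that coding keeps it as a laboratory term. The case is clearest for GFR and creatinine. For urea it is weaker, because azotaemia is on the list and the documents do not say how a urea rise would be coded.

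The undercount cannot be computed, since the documents do not say how often such AEs would be recorded. It is 2 percentage points per omitted child at 50 subjects. It would be wrong to infer that the renal rate is understated by any stated amount, or that the primary safety analysis fails.

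**What to change.** In SAP Table 9.b, add the preferred terms for decreased GFR or creatinine clearance and for increased blood creatinine or urea, using the exact names and codes of the MedDRA version cited there. In summary 7.11.1.2 (11), show three rows: the currently listed terms, the laboratory-coded terms, and a total counting each subject once. Reconcile the Protocol 10.2.1.3 list with Table 9.b so that reporting and analysis use one definition.

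The analysis change needs no new data and alters no hypothesis; the Table 9.c cut-offs can stay as they are. The downside is slightly higher reported renal counts, which the separate rows make interpretable, and a few more special-interest forms if the protocol list is aligned.

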9.2 Criteria for Markedly Abnormal Values

For each test item, MAV will be determined according to the table below for evaluable data (i.e., non-missing data) obtained within 14 days after the last study drug administration for the Treatment Period (including Day 14 after the last study drug administration for the Treatment Period; the day after the last study drug administration for the Treatment Period to be defined as Day 1). The lower limit of the normal range and the upper limit of the normal range of each test item are abbreviated as LLN and ULN in the table below.

Table 9.c MAV Criteria for Serum Chemistry

Test Item	Gender	Age (years)	MAV Criteria	
			Lower	Upper
BUN (mg/dL)	-	-	-	> 30
Chloride (mEq/L)	-	-	< 75	> 126
Creatinine (mg/dL)	-	-	-	> 2.0
Potassium (mEq/L)			< 3.0	> 6.0
Sodium (mEq/L)			< 130	> 150
eGFR (mL/min/1.73 m ²)			< 30	
ALT (IU/L)	-	-	-	> 3 × ULN
AST (IU/L)	-	-	-	> 3 × ULN
GGT (IU/L)	-	-	-	> 3 × ULN
Total bilirubin (mg/dL)	-	-	-	> 2.0
Creatinine kinase (U/L)				> 5×ULN

Classifying Subjects for the Overall Treatment Period

For each test item and subject, MAV will be determined according to the conditions [1] to [3] provided below. If there are criteria for "Upper" and "Lower" in the MAV Criteria for the same test item, the determination will be made for each criterion.

- [1] A subject will be classified as those "with MAV" if he/she has at least one data that "meets the MAV Criteria" among the evaluable data obtained after the study drug administration for the Treatment Period.
- [2] A subject will be classified as those "without MAV" if he/she does not meet condition [1] and has at least one data that does "not meet the MAV Criteria" among the evaluable data obtained after the study drug administration for the Treatment Period.
- [3] A subject who does not meet conditions [1] or [2] will be excluded from the analysis of MAV for that item.

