6.2 Justification for Study Design, Dose, Regimen, and Endpoints

[Justification for the Study Design]

Many pediatric patients with renal dysfunction are assumed to be entered this study since the proportion of pediatric patients with secondary hypertension caused by renal disease is high in pediatric patients with hypertension. Evidence-based Clinical Practice Guideline for CKD 2013 (JSN2013) [9] indicates that treatment with ARB should be start at a low dose in patients with renal dysfunction and the dose should be increased with caution by confirming the hypotensive effect of ARB and renal function. On the basis of above indication, an open-label, optional titration

design was selected in this study, in which TAK-536 can be titrated with monitoring subject condition.

Co-administration of RAS inhibitors, which is similar to TAK-536, is prohibited in order to evaluate appropriately the efficacy of TAK-536 in the pediatric patients throughout the Run-in Period and the Treatment Period I. In consideration of the safety for vulnerable pediatric population, subjects can continue to receive a single antihypertensive drug other than RAS inhibitors in the same dosage after the start of the Run-in Period, if the subjects are considered to need the additional treatment for hypertension by the investigator or subinvestigator. In the Treatment Period II, the subjects whose blood pressure is not reduced sufficiently by TAK-536 can receive additional antihypertensive drugs other than RAS inhibitors concomitantly in order to evaluate the efficacy and safety of the long-term administration of TAK-536 in pediatric patients under the condition of being closer to the routine medical care.

The Run-in Period with placebo was selected to wash out the placebo effect of the study drug and the influence of antihypertensive drugs as a prior treatment in subjects who were treated with any prior antihypertensive drugs. In addition, the Run-in Period allows the opportunity to assess subject compliance with the study drug (i.e., placebo) and subjects who are not sufficiently compliant with placebo will be excluded.

The Follow-up Period was selected to evaluate the subject safety after the study drug administration.

[Justification for the Doses]

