7.11.2 Clinical Laboratory Evaluations

7.11.2.1 Hematology and Serum Chemistry

Analysis Set:

Safety analysis set

Analysis variable(s):

Hematology

Red blood cell count, White blood cell count with differential (neutrophils, basophils, eosinophils, lymphocytes, monocytes), Hemoglobin, Hematocrit, Platelets

Serum Chemistry

ALT, Albumin, ALP, AST, Total bilirubin, BUN, Calcium, Chloride, Creatinine, Creatinine kinase, Cystatin C, eGFR, GGT, Glucose, Total cholesterol, Triglycerides, Phosphate, Potassium, Sodium, Total Protein, LDH

Categories:

Results of determination based on normal reference range [Below lower limit of normal range, Within normal range, Over upper limit of normal range]

Visit:

Weeks 0, 2, 4, 8, 12, 16 (postdose), 24, 40, and 52

Analytical method(s):

The following analysis will be performed for the above analysis variables by weight group ($< 50 \text{ kg}, \ge 50 \text{ kg}$) and in the combined weight groups.

When performing analyses on MAV, if a laboratory parameter has both lower and upper MAV criteria, an analysis will be performed for each. See "9.0 APPENDIX" for test items to be analyzed and definitions of MAV criteria.

The measurement at Week 16 will be performed after the study drug administration, while the measurement at other visits than Week 16 will be performed before the study drug administration.

- (1) Summary statistics for observed values and changes (each visit after administration [Week 2 to Week 52] Week 0) will be provided for each visit.
- (2) Case Plots
- (3) Shift tables showing results of determination based on normal reference range at Week 0 and each visit after administration
- (4) Overall frequency distributions of MAV during the Treatment Period

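### The markedly-abnormal-value rule in SAP 9.2 ignores Week 0, so the creatinine and BUN rows cannot separate new crossings from abnormality carried over from entry

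*SAP*

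**What the plan says.** SAP 9.2 sets fixed limits for eleven serum chemistry items. The upper limits include creatinine above 2.0 mg/dL and BUN above 30 mg/dL, the same for every age, sex and height. Classification is per child and per item. Condition [1] makes a child a case on one qualifying value: "A subject will be classified as those 'with MAV' if he/she has at least one data that 'meets the MAV Criteria' among the evaluable data". The values searched are those "among the evaluable data obtained after the study drug administration for the Treatment Period", up to 14 days after the last dose. Condition [2] covers children with post-dose data that never cross the limit. Condition [3] deals with the rest: "A subject who does not meet conditions [1] or [2] will be excluded from the analysis of MAV for that item". Since anyone with a post-dose value falls under [1] or [2], only children with no evaluable post-dose value drop out. No condition refers to Week 0.

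SAP 7.11.2.1, item (4), reports the result as "Overall frequency distributions of MAV during the Treatment Period". The same section also plans summaries of change from Week 0, case plots, and item (3): "Shift tables showing results of determination based on normal reference range at Week 0 and each visit after administration".

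On the population, protocol 6.2 states: "Many pediatric patients with renal dysfunction are assumed to be entered this study". Exclusion criterion 6 in protocol 7.2 removes children with eGFR below 30, and inclusion criterion 7 in protocol 7.1 admits stable kidney transplant recipients at eGFR 30 or above. Neither list of criteria contains a numerical limit on creatinine or BUN.

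**The concern.** Laboratory tests are among the primary safety endpoints, and the study has one arm. With no control group, each child's own Week 0 value is the only reference for what changed on treatment. The MAV table is the only planned laboratory table built on fixed limits of concern, and it does not use that reference. A child whose creatinine was above 2.0 mg/dL before the first dose and stays there is counted exactly like a child who crosses the limit on treatment.

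The adverse event rules do make this distinction. Protocol 10.1.2 says: "Pre-existing conditions (present at the time of signing of informed consent) are considered concurrent medical conditions and should NOT be recorded as AEs", and treatment-emergent events must begin after dosing. The MAV table has no equivalent.

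What is at stake is how two renal rows are read. Renal dysfunction is named as an adverse event of special interest (protocol 10.2.1.3). SAP 7.12 also puts section 7.11.2.1 into the Week 12 analysis of about 25 subjects, which is meant to inform the design of the study in children under 6 and goes into regulatory consultation material.

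**Working it through.** **The plan's own figures.** The documents give no expected MAV rate, so there is none to reproduce. The only design figure is power. With n = 50 and two-sided alpha 0.05, the one-sample t-test has power 99.0% for diastolic pressure (change -6.5, SD 10.5) and 98.9% for systolic (change -9.5, SD 15.5). The stated minimum of 90% is met, and this point does not affect it.

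**Step 1: can an eligible child already be above creatinine 2.0?** Protocol 9.1.9 gives eGFR = 110.2 × S / Cr + 2.93, where Cr is serum creatinine and S is the standard creatinine, a fifth-degree polynomial in height with separate coefficients for boys and girls. Setting eGFR = 30 and Cr = 2.0 gives the smallest S that allows both:

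S = 2.0 × (30 - 2.93) / 110.2 = 0.491 mg/dL.

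Solving the polynomials for that value gives a height of 1.460 m (boys) and 1.492 m (girls). Across heights (boy / girl):

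| Height | S (mg/dL) | eGFR at Cr 2.0 | Highest Cr with eGFR 30 |
|---|---|---|---|
| 1.20 m | 0.361 / 0.361 | 22.8 / 22.8 | 1.47 / 1.47 |
| 1.40 m | 0.453 / 0.437 | 27.9 / 27.0 | 1.85 / 1.78 |
| 1.50 m | 0.520 / 0.497 | 31.6 / 30.3 | 2.12 / 2.02 |
| 1.60 m | 0.602 / 0.562 | 36.1 / 33.9 | 2.45 / 2.29 |
| 1.70 m | 0.699 / 0.609 | 41.5 / 36.5 | 2.85 / 2.48 |

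Shorter children cannot exceed 2.0 without failing the eGFR criterion. Taller children can, and the eGFR band in which this happens widens with height: 30 to 31.6 for a boy of 150 cm, 30 to 41.5 for a boy of 170 cm.

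**Step 2: BUN.** The eGFR formula does not contain BUN and no criterion limits it, so BUN above 30 mg/dL is possible at entry at any height.

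**Step 3: what the rule does with such a child.** Take a boy of 170 cm with creatinine 2.6 at Week 0 and 2.2 on treatment (assumed values). His eGFR goes from 110.2 × 0.699 / 2.6 + 2.93, about 33, to 110.2 × 0.699 / 2.2 + 2.93, about 38. He has improved, yet condition [1] counts him as a case.

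**Step 4: do other outputs separate him?** In the normal-range shift table he goes from above the upper limit to above the upper limit. So does a child who moves from a mildly raised creatinine to above 2.0. Summaries of change do not identify individuals. Case plots show each course but give neither a count nor a denominator.

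**Step 5: effect on the table.** Let k be the number of children above the limit at Week 0 who stay above it after dosing, and m the number who newly cross. Both are assumed, and every child is taken to have Week 0 and post-dose data. The SAP rule reports (k + m)/50; the new-case proportion is m/(50 - k).

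| k | m | SAP rule | New cases among those at risk |
|---|---|---|---|
| 0 | 2 | 4% | 2/50 = 4% |
| 2 | 0 | 4% | 0/48 = 0% |
| 2 | 2 | 8% | 2/48 = 4.2% |
| 5 | 0 | 10% | 0/45 = 0% |
| 5 | 2 | 14% | 2/45 = 4.4% |

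Each carried-over child adds 1/50 = 2 percentage points to the SAP figure, or 1/25 = 4 points in a Week 12 analysis of 25. With k = 0 the two figures agree.

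**The case against.** The strongest reply is that the SAP's label is literally accurate: the table shows values beyond a limit during the Treatment Period and is never called new or treatment-emergent. Week 0 is collected, changes and individual plots are planned for the same analytes, and with about 50 children a reader could trace each one. This stands in part. The information will exist; what is missing is a pre-specified count. A reader might infer that the trial could not say how many children newly became markedly abnormal. The documents do not support that, because the count could be made from data already planned.

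It can also be said that the renal rows are not all affected. This stands. Entry excludes eGFR below 30 and potassium above the upper limit of normal at screening, so a baseline MAV for low eGFR or high potassium is largely ruled out. The entry limits on ALT/AST and bilirubin do the same for those rows. Because eGFR here depends only on creatinine, height and sex, the eGFR row is already close to a height-adjusted count of new creatinine-based cases.

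Finally, new clinical deterioration has its own route. Protocol 10.1.2 goes on to require that worsening of a concurrent condition be recorded as an adverse event, and SAP 7.11.1.2 tabulates renal dysfunction events separately. This also stands, but it relies on clinical judgement and reporting, and it does not make the laboratory table easier to read.

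**Conclusion.** The concern holds for the creatinine and BUN rows. The rule does not consult Week 0, the entry criteria leave room for children already above both limits, and no planned table counts new crossings. The creatinine route is open only to children of at least about 146 cm (boys) or 149-150 cm (girls) in a limited eGFR band; the BUN route is open at any height.

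The size is 2 percentage points per carried-over child at n = 50 and about 4 at n = 25. The number of such children cannot be derived. That many children with renal dysfunction are expected does not say how many are tall enough and in the right eGFR band, or have BUN above 30, and the answer may be none. A reader might put a definite inflation on the table; the documents give no baseline frequency to support one.

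Two other stronger readings also fail. Entering above a limit does not by itself make a child a case, because a post-dose value must also exceed it. And although the home blood pressure rule in SAP 9.3 has the same structure, exclusion criterion 3 bars children at the same margins on office readings, so a similar carry-over there has not been shown.

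**What to change.** Leave the thresholds in SAP 9.2 as they are. In 9.2 and in 7.11.2.1 item (4), add a classification of each child's Week 0 value against the same limit, item by item, as absent, present or missing. Report as the main count the children without MAV at Week 0 who meet the criterion after dosing, with children without MAV at Week 0 who have evaluable post-dose data as the denominator. Show children already meeting it at Week 0 on a separate line with their post-dose status, and those with no Week 0 value on another. Use the same layout in the Week 12 analysis.

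The cost is a few lines of SAP wording and one split in an existing table. No new data are needed, because Week 0 laboratory values are already collected. The one drawback is a slightly smaller denominator for the new-MAV count.
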